5.4.2.1 Calculation of change from baseline

Baseline is defined as the last measurement before the first dose of pembrolizumab or birinapant. The change from baseline value for visit X is derived as ‘value at visit X’ minus ‘value at baseline’.

5.4.3 *Interim Analysis and Data Monitoring*

An independent Data Monitoring Committee (DMC) will meet approximately biannually during the dose expansion phase to review the complete analysis of combined observed toxicities including emerging safety reports and reported SAEs.

Predefined interim analyses for fertility and safety will be conducted in each of the cohorts in colorectal cancer, ovarian cancer and cervical cancer to limit undue exposure before further inclusion into a given cohort.

The interim analysis constitutes the first stage in Simon’s two-stage design controlling the overall type I error to 5% within each cohort. The interim analysis for each of the three cohorts will be as follows:

5.4.3.1 Colorectal Cancer Cohort

The interim analysis will be based on at least 6 and most 13 patients having completed from 9 up to 27 weeks of treatment (3 to 9 cycles) in the colorectal cancer cohort.

The second stage will continue, i.e. the remaining patients in the cohort will be recruited according to the plan, if at least 1 patient (out of 6-13 patients) responds in the overall tumor response assessed through RECIST v1.1. (provided the DMC decides not to stop the second stage because of safety issues).

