12.2 Determination of Sample Size

No formal sample size or power calculations will be performed for the dose-escalation phase of the study. A sample size of 3 to 6 patients per cohort is a feasible sample size to assess safety for dose escalation and dose-limiting toxicity. Additional patients may be needed for cohort expansion during dose escalation, for the replacement of non-evaluable patients. Only patients who do not complete the first cycle due to study drug related toxicity will be replaced.

Once the RP2D of birinapant combined with pembrolizumab is defined, additional patients with relapsed or refractory carcinoma will be enrolled in the dose-expansion phase of the study.

The dose expansion phase will comprise 4 cohorts of 26-30 patients, as follows:

- Colorectal cancer (28 patients)
- Ovarian cancer (27 patients)
- Cervical cancer (26 patients)
- Various solid tumors (30 patients, including 5 patients with each of the 6 following tumor types: (Small cell lung cancer; Cholangiocarcinoma; Gastroesophageal carcinoma; Mesothelioma; Head and Neck Squamous Cell Carcinoma (HNSCC)-checkpoint inhibitor-naïve; and HNSCC checkpoint inhibitor-experienced)

A Simon's 2-stage design (Simon 1989) will be used for each of the cohorts in colorectal cancer, ovarian cancer and cervical cancer, as outlined in Table 17. A predefined interim analysis allowing stopping each of these cohorts for futility and safety will be conducted in the first stage to limit undue exposure before further inclusion into a given cohort.

The interim analyses will be based on at least 6 and most 13 patients having completed from 9 up to 27 weeks of treatment (3 to 9 cycles) in the colorectal cancer cohort and based on at least 6 and at most 16 and 15 patients in the ovarian cancer cohort and

cervical cancer cohort, respectively. Note that one additional patient will be included in each cohort. This patient will only be included in the interim analysis in case a patient drops out in that cohort. Thus, the number of included patients in each cohort will be 27+1 (CRC), 26+1 (ovarian) and 25+1 (cervical). In all cases this extra patient will be included in the main/end analysis. If the predefined level for success in a given cohort is reached prior to the stipulated number of patients being enrolled/completed, enrollment in that cohort may be discontinued.

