12.7 Efficacy Analysis

Efficacy, as measured by the ORR, will be assessed through RECIST v1.1 and iRECIST measurements and clinical response per Investigator. Results will be summarized descriptively (See SAP for further details).

In the dose expansion phase of the protocol, the null hypothesis that the true response rate is p_0 will be tested against the one-sided alternative $H_A: ORR > p_0$ in each of the three cohorts in Simon’s two-stage design (Simon 1989). The statistical test will be performed for each cohort with p_0, p_1, n_1, n, r_1 and r_2 as in Table 17 as follows. In the first stage, n_1 patients will be accrued. If there are r_1 or fewer responses in these n_1 patients, the study will be stopped. Otherwise, $n - n_1$ additional patients will be accrued for a total of n patients. The null hypothesis will be rejected if $r_2 + 1$ or more responses are observed in n patients. This design yields a type I error rate of 0.05 and power of 0.80 when the true response rate is p_1 for each of the three main cohorts. No correction for multiple comparisons are done.

Table 17 Simon’s two-stage design settings in each of the three main cohorts

Indication	Response rate (ORR)		n_1 (# patient in the 1st stage)	n (Total #patients)	r_1 (Continue with stage 2 if $>r_1$ responses in stage 1)	r_2 (p-value ≤ 0.05 if $>r_2$ responses after stage 2)
	Poor drug (p_0)	Good drug (p_1)				
Colorectal cancer	$\leq 5\%$	$\geq 20\%$	13	27	0	3
Ovarian cancer	$\leq 7\%$	$\geq 25\%$	16	26	1	4
Cervical cancer	$\leq 10\%$	$\geq 30\%$	15	25	1	5

Note that one additional patient will be included in each cohort. This patient will only be included in the interim analysis in case a patient drops out in that cohort. Thus, the number of included patients in each cohort will be 27+1 (CRC), 26+1 (ovarian) and 25+1 (cervical). In all cases this extra patient will be included in the main/end analysis. The final statistical analysis will take account of the actual number of patients evaluable for efficacy.

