3.3.1.2 Dose expansion phase

The dose expansion phase will comprise 4 cohorts of 26-30 patients, as follows:

1. Colorectal cancer (28 patients will be recruited)
2. Ovarian cancer (27 patients will be recruited)
3. Cervical cancer (26 patients will be recruited)
4. Various solid tumors (30 patients will be recruited, including 5 patients with each of the 6 following tumor types: (Small cell lung cancer; Cholangiocarcinoma; Gastroesophageal carcinoma; Mesothelioma; Head and Neck Squamous Cell Carcinoma (HNSCC)-checkpoint inhibitor-naïve; and HNSCC checkpoint inhibitor-experienced)

A Simon's 2-stage design (Simon 1989) will be used for each of the cohorts in colorectal cancer, ovarian cancer and cervical cancer, as outlined in Table 4. A predefined interim analysis allowing stopping each of these cohorts for futility and safety will be conducted in the first stage to limit undue exposure before further inclusion into a given cohort.

The interim analyses will be based on at least 6 and most 13 patients having completed from 9 up to 27 weeks of treatment (3 to 9 cycles) in the colorectal cancer cohort and based on at least 6 and at most 16 and 15 patients in the ovarian cancer cohort and cervical cancer cohort, respectively.

The Simon's two-stage design as outlined in Table 4 yields a type I error rate of 0.05 and statistical power of 0.80 for each of the three main cohorts described above using a one-sided test when the true response rate is 20% for colorectal cancer, 25% for ovarian cancer and 30% for cervical cancer. No formal sample size or power calculation will be performed for the fourth cohort.

Note that one additional patient will be included in each cohort compared to what is stated in Table 4. This patient will only be included in the interim analysis in case a patient drops out in that cohort. Thus, the number of included patients in each cohort will be 27+ 1 (CRC), 26+1 (ovarian) and 25+1 (cervical). In all cases this extra patient will be included in the main/end analysis. If the predefined level for success in a given cohort is reached prior to the stipulated number of patients being enrolled/completed, enrollment in that cohort may be discontinued.

4. Assessments

An overview of the time points of measurements for each assessment is given in Table 5 (Schedule of Study Procedures and Assessments) in Appendix 1.

4.1 *Disposition and Other Supporting Assessments*

4.1.1 *Patient Compliance*

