4.2.3.1 Overall response (and ORR) assessed through RECIST 1.1

The primary endpoint in the dose expansion phase is the overall response assessed through RECIST v.1.1 until response or progression. A patient with a best overall response of either CP or PR is defined as a patient with an overall response according to RECIST 1.1. A tumor measurement categorized as CP or PR needs a confirmed response of either CP or PR at least 4 weeks after the initial response assessment to be classified as best overall response CP or PR. Examples of patients with an overall response are the following (observations in cycle 3 (week 9) and subsequent every 3rd cycles (9 weeks between each measurement)):

- SD, SD, PR, PR, ; SD, SD, PD (overall response as PR in cycle 9 which is confirmed in cycle 12 (9 weeks after))
- SD, SD, SD, CR, CR (overall response as CR in cycle 12)

Example of patients with no overall response as assessed through RECIST 1.1:

- SD, SD, SD, SD, SD, SD, SD, SD, SD
- SD, PD(iUPD), iSD, iSD, iCPD
- SD, PD(iUPD), iSD, iSD
- SD, SD, PR, SD, SD, PD (PR in cycle 9 is not confirmed)
- SD, PD(iUPD), iPR, iSD, iSD (no overall response according to RECIST 1.1)

The overall response rate (ORR) is defined as the proportion of patients that are classified as overall responders assessed through RECIST 1.1 as described above.

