5.4.3.2 Ovarian Cancer Cohort

The interim analysis will be based on at least 6 and most 16 patients having completed from 9 up to 27 weeks of treatment (3 to 9 cycles) in the ovarian cancer cohort.

The second stage will continue if at least 2 patients (out of 6-16 patients) respond in the overall tumor response assessed through RECIST v1.1. (provided the DMC decides not to stop the second stage because of safety issues).

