5.4.3.3 Cervical Cancer Cohort

The interim analysis will be based on at least 6 and most 15 patients having completed from 9 up to 27 weeks of treatment (3 to 9 cycles) in the cervical cancer cohort.

The second stage will continue if at least 2 patients (out of 6-16 patients) respond in the overall tumor response assessed through RECIST v1.1. (provided the DMC decides not to stop the second stage because of safety issues).

5.4.4 *Multiple Comparisons/Multiplicity*

The four cohorts will be handled separately, no adjustment for multiple comparisons will be made between cohorts. No adjustment for multiple comparisons will be performed within a cohort as there is only one primary endpoint in each of the three main cohorts.

For the secondary efficacy variables, no statistical inference will be performed. Thus, no adjustment for multiple comparisons will be made.

5.4.5 *Examination of Subgroups*

No pre-defined analysis on subgroups are planned.

5.5 *Patient Disposition Summary*

Descriptive summaries for continuous data and for categorical data will be provided in accordance with Section 5.3 if other not stated.

5.5.1 *Patient Disposition*

Number of patients screened, enrolled, discontinued for treatment (by reason), continuing in follow-up, and discontinued from the study (by reason) will be summarized by cancer cohort.

5.5.2 *Protocol Deviations*

Protocol deviations will be displayed in listings.

5.5.3 *Demographic and Baseline Characteristics*

Demographics and baseline characteristics (gender, age, ethnicity, race, height, weight and body surface area) will be presented as a table for the screening visit.

5.5.4 *Medical History*

Medical history and medical conditions ongoing at Screening will be coded by system organ class (SOC) and preferred term (PT) using MedDRA (version 20.0) and presented as number and percentage of patients in each SOC and PT by cancer cohort and in total over cohorts.

5.5.5 *Prior and Concomitant Medications*

Prior and concomitant medication will be coded according to the WHO-Drug Dictionary Enhanced (Version Mar 2017) and ATC classification. Prior and concomitant medication will be reported as a listing for all enrolled patients and tabulated by ACT level 1 and level 3 by cancer cohort and in total over cohorts.

Prior anti cancer therapies, prior medications and concomitant medications will be tabulated separately.

5.5.6 *Exposure to Study Treatment*

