5.6.1 Primary Efficacy Analysis

The primary endpoint will be summarized for the Efficacy Evaluable Population in accordance with Section 5.3.

The primary efficacy analysis for each of the three main cohorts in the dose expansion phase of the protocol will be evaluated using Simon’s two-stage design (Simon 1989). The null hypothesis that the true response rate (π) is π_0 will be tested against the one-sided alternative $H_A: \pi > \pi_0$ in each of the three cohorts with π_0 , π_1 , n_1 , n , r_1 and r_2 as in Table 4 as follows. In the first stage, n_1 patients will be accrued. If there are r_1 or fewer responses in these n_1 patients, the cohort will be stopped and the p-value for the test will be reported as not significant (no p-value will be calculated). Otherwise, $n - n_1$ additional patients will be accrued for a total of n patients. The null hypothesis will be rejected if r_2+1 or more responses are observed in n patients.

Table 4 Simon’s two-stage design settings in each of the three main cohorts

Indication	Response rate (ORR)		n_1 (# patient in the 1 st stage)	n (Total #patients)	r_1 (Continue with stage 2 if $>r_1$ responses in stage 1)	r_2 (p-value ≤ 0.05 if $>r_2$ responses after stage 2)
	Poor drug (π_0)	Good drug (π_1)				
Colorectal cancer	$\leq 5\%$	$\geq 20\%$	13	27	0	3

Ovarian cancer	$\leq 7\%$	$\geq 25\%$	16	26	1	4
Cervical cancer	$\leq 10\%$	$\geq 30\%$	15	25	1	5

In case the total number of evaluable patients do not equal the planned number of patients (n in Table 4), the statistical inference of the ORR will take account of the actual total number of evaluable patients, n^* , as suggested in Koyama and Chen (2007). With a modified stage 2 sample size, the p-value will be calculated as follows.

- i. Find π^* such that $P_{\pi}(X_2 > r_2 - x_1 | n_2) = P_{\pi_0}(X_2 \geq x_2 | n_2^*)$
- ii. Compute the p-value by

$$\sum_{x=r_1+1}^{n_1} P_{\pi_0}(X_1 = x | n_1) A(x, n_2, \pi^*)$$

Here $n_2 (= n - n_1)$ denotes the planned number of patients in the second stage, n_2^* the actual number of patients in the second stage and X_2 denotes the number of responses among those n_2 patients. The p-value will be calculated as above even if $n_2^* = n_2$. In that case it simplifies to the original Simon's 2-stage design with rejection regions as in Table 4.

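### The futility decision may rest on as few as 6 patients with cut-offs built for 13, 16 and 15, so the stated 80% power is not assured with fewer than about 11, 14 and 13 resolved patients

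*SAP*

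**What the plan says.** SAP Table 4 and Protocol Table 17 fix the first stage (n1) at 13, 16 and 15 patients for colorectal, ovarian and cervical cancer, with r1 = 0, 1 and 1. Protocol 12.7 applies the stop to that full group: "If there are r_1 or fewer responses in these n_1 patients, the study will be stopped". SAP 5.6.1 uses the same denominator and adds that "the cohort will be stopped and the p-value for the test will be reported as not significant".

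The interim sections say something else. SAP 5.4.3.1: "The interim analysis will be based on at least 6 and most 13 patients having completed from 9 up to 27 weeks of treatment". SAP 5.4.3.2, for ovarian cancer: "The second stage will continue if at least 2 patients (out of 6-16 patients) respond". SAP 5.4.3.3 bases the cervical look on "at least 6 and most 15 patients having completed from 9 up to 27 weeks of treatment (3 to 9 cycles"), yet its next sentence gives the denominator as 6 to 16. SAP 3.3.1.2 and Protocol 12.2 repeat the minimum of 6. SAP 5.4.3 describes this interim as the first stage of the Simon design, so it is the futility decision and not an additional safety look.

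Power is stated without conditions: the design "yields a type I error rate of 0.05 and statistical power of 0.80 for each of the three main cohorts" (SAP 3.3.1.2). For the primary endpoint, a CR or PR "needs a confirmed response of either CP or PR at least 4 weeks after the initial response assessment" (SAP 4.2.3.1), and the first scan is at week 9. Each cohort also enrols one spare patient, of whom Protocol 12.2 says: "This patient will only be included in the interim analysis in case a patient drops out in that cohort".

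**The concern.** A cut-off of 1 or 2 responders is lenient among 13 to 16 patients and demanding among 6. Keeping it while the denominator shrinks makes a futility stop more likely whether or not the combination works. Nothing in either document scales the cut-off, or sends a cohort that misses it among fewer than n1 patients on to n1 before stopping. The Koyama–Chen adjustment in SAP 5.6.1 deals with a changed total or stage-2 size, not a shortened first stage.

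Maturity adds to this. The look admits patients with 9 weeks of treatment, and a patient between weeks 9 and 12 cannot yet have a confirmed response.

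At stake is an active combination being dropped in an indication more often than the plan states, by a committee holding two different rules. A wrongful stop cannot be repaired at the final analysis.

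**Working it through.** **Inputs.** From SAP Table 4, as colorectal / ovarian / cervical: null ORR p0 = 5/7/10%; target ORR p1 = 20/25/30%; n1 = 13/16/15; n = 27/26/25; r1 = 0/1/1; r2 = 3/4/5. Enrolment time to interim is 4/8/8 months (Protocol 3.3).

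**Formulas.** For an interim on m patients with r1, r2 and n unchanged:

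- P(stop) = P(Bin(m, p) ≤ r1)
- P(reject) = Σ over x > r1 of P(Bin(m, p) = x) × P(Bin(n − m, p) > r2 − x)

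**The plan's own figure.** With m = n1, power is 0.801/0.803/0.802 and type I error 0.042/0.031/0.033. The stated 0.80 reproduces.

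**Smaller looks at the target ORR.** At m = 6 the chance of a wrongful stop is:

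- colorectal: 0.8^6 = 0.262
- ovarian: 0.75^6 + 6 × 0.25 × 0.75^5 = 0.178 + 0.356 = 0.534
- cervical: 0.7^6 + 6 × 0.3 × 0.7^5 = 0.118 + 0.303 = 0.420 (after rounding)

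| Interim size | Power: colorectal | Ovarian | Cervical |
|---|---|---|---|
| 6 | 0.65 | 0.44 | 0.53 |
| 8 | 0.73 | 0.58 | 0.66 |
| 10 | 0.77 | 0.68 | 0.74 |
| 11 / 14 / 13 | 0.78 | 0.78 | 0.79 |
| 13 / 16 / 15 (planned) | 0.80 | 0.80 | 0.80 |

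Type I error at 6 patients is 0.030/0.011/0.016, below the planned values. The chance of stopping an inactive combination (at p0) is 74%/94%/89% at 6 patients, against 51%/69%/55% as planned.

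**Is a small look likely?** Assume even accrual, with 52/12 weeks per month and n1 or n1 − 1 equal intervals. One patient then enters every 1.33–1.44 / 2.17–2.31 / 2.31–2.48 weeks. When the first patient reaches week 27, the upper limit in SAP 5.4.3, those who entered in the first 27 − 9 = 18 weeks have completed week 9. That is all 13 in colorectal, 8–9 in ovarian and 8 in cervical. In the last two cohorts the n1-th patient reaches week 9 only when the first is at about week 41–44.

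**Immaturity.** Count patients not yet at week 13 as non-responders at the look, with the same accrual.

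- Look taken when the n1-th patient reaches week 9: about 10/14/13 are at week 13 or later, and power is 0.77/0.78/0.79.
- Look taken when the 6th patient reaches week 9: about 3/4/4 are, and power is 0.44/0.25/0.32.

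**The case against.** The best defence is that the range of 6 to n1 counts those of the n1 enrolled patients who are still on treatment at week 9, the rest having left early as non-responders. Then 1/2/2 responders among the completers is the same rule as r1 = 0/1/1 among n1, and power is kept. Protocol 3.3 fits this: splitting enrolment at n1 gives steady accrual of 13/4 = 3.25 then 14/4 = 3.5 patients per month in colorectal, 16/8 = 2.0 then 10/5 = 2.0 in ovarian, and 15/8 = 1.9 then 10/5 = 2.0 in cervical. The spare-patient rule also presumes a fixed n1. So a 6-patient look is probably not what is intended. But neither document states this reading, and the words as written permit the smaller look.

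Two further points have some force. The DMC may delay the interim by up to 4 months (Protocol 3.1.4), and 27 + 17.3 = 44.3 weeks would just cover the 41–44 weeks needed. That delay is optional and turns on judged patient benefit, not on reaching n1. The spare patient enters the final analysis: with n = 28/27/26 and r2 unchanged, power is at least 0.80 from 11/14/12 patients. At 6 patients it is still only 0.665/0.441/0.538.

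The 27-week limit binds only if the earliest patients are still on treatment, and the 0.44/0.25/0.32 figures combine the smallest look with the earliest moment. They mark the extreme, not the expected case.

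**Conclusion.** The concern holds. The documents contain two stage-1 rules, and the one in SAP 5.4.3 does not deliver the unconditional 0.80. Over the permitted range, power runs from 0.65/0.44/0.53 at 6 patients with mature outcomes up to 0.80 at n1. It is within 2 points of 0.80 only from 11/14/13. At 6 patients, a combination that truly meets the 25% ovarian target would more likely than not be stopped.

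These figures assume that a cohort stops when it misses the cut-off among the patients seen, and that r1, r2 and n stay as tabulated. The timing and immaturity figures also assume even accrual. Because the text could be applied at full n1, power is not assured rather than certainly lost. Type I error is not inflated, and the planned p-value stays valid, if conservative. The point still needs correcting before any interim, because this rule decides each cohort's fate on the primary endpoint.

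**What to change.** 1. In SAP 5.4.3.1–5.4.3.3, SAP 3.3.1.2 and Protocol 12.2, allow a futility stop only on n1 = 13/16/15 patients whose confirmed-response status is resolved: confirmatory window passed, progression, or death. Fix the assessment at which stable disease counts as resolved; the tabulated power then refers to response by that time. Cover one dropout by the existing spare-patient rule and say how any further dropout counts.
2. Keep earlier looks as continue-only: stage 2 may open once more than r1 confirmed responses are seen. More than r1 among the first few patients guarantees more than r1 among n1, so type I error and power stay exactly as tabulated (full enumeration of a continue-only look at 6 confirms this). Hold stage 2 enrolment closed until item 1 or 2 is met, including while a first CR or PR awaits its confirmatory scan.
3. In SAP 5.4.3.2 and 5.4.3.3, drop or extend the 27-week upper limit so that n1 can be reached at planned accrual.
4. In SAP 5.4.3.3, bring the 6 to 16 denominator into line with the maximum of 15.

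If the sponsor prefers smaller looks, state the power for each permitted interim size in place of 0.80.

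The cost is wording, with no patients beyond the planned n1. Compared with a 6-patient look, a futility stop could come about 2 months later in colorectal and 5 months later in ovarian and cervical, with 7/10/9 more patients treated first, plus about 4 weeks if the last patient awaits confirmation. What is given up is the more frequent early stopping of an inactive combination shown in the working.

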The primary objective will be evaluated using Simon's two-stage design. The null hypothesis that the true ORR is (5%, 7% and 10% for colorectal cancer, ovarian cancer and cervical cancer, respectively) will be tested against a one-sided alternative. The design yields a type I error rate of 5% and power of 80% for each of the three indications individually. No correction for multiplicity will be done. In addition to tabulate the result of the statistical tests, results will be summarized descriptively.

Various solid tumors cohort: Safety

The safety and tolerability of pembrolizumab and birinapant will be based on results of reported SAEs, AEs, vital sign measurements, physical examinations, clinical laboratory information, ECOG performance status, and concomitant medications. Safety data will be summarized descriptively. Exposure to study drug and reasons for discontinuation will be tabulated.

Adverse events will be coded using the current *Medical Dictionary for Regulated Activities* (MedDRA) classification system, and will be summarized by system organ class and preferred term.

Additional safety analyses may be determined in order to most clearly describe toxicity rates and to further define the

safety profile of pembrolizumab and birinapant.

Secondary Endpoints:

Cohorts in colorectal cancer, ovarian cancer and cervical cancer: Safety

The safety and tolerability of pembrolizumab and birinapant will be based on results of reported SAEs, AEs, vital sign measurements, physical examinations, clinical laboratory information, ECOG performance status, and concomitant medications. Safety data will be summarized descriptively by cohort and also summarized descriptively over cohorts within each of the two phases of the protocol. Exposure to study drug and reasons for discontinuation will be tabulated.

Adverse events will be coded using the current *Medical Dictionary for Regulated Activities* (MedDRA) classification system, and will be summarized by system organ class and preferred term.

Additional safety analyses may be determined in order to most clearly describe toxicity rates and to further define the safety profile of pembrolizumab and birinapant.

All Cohorts: Clinical Activity

Efficacy, as defined by PFS, CBR, Time to response and Duration of response, will be assessed through RECIST v 1.1 and until response or progression. Overall survival will also be assessed.

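### The interim futility set (6 to n1 nine-week completers, one spare for a drop-out) contradicts the Simon stage 1 of n1 accrued patients, so the stated operating characteristics do not belong to the rule as written

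*SAP*

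**What the plan says.** Two definitions of stage 1 stand side by side.

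- **Design definition.** Protocol 12.7 accrues n1 patients and then applies the cut-off: "If there are r_1 or fewer responses in these n_1 patients, the study will be stopped". SAP 5.6.1 has the same rule at cohort level. Table 17 of the protocol and Table 4 of the SAP give n1/n/r1/r2 as 13/27/0/3 (colorectal), 16/26/1/4 (ovarian) and 15/25/1/5 (cervical). SAP 3.3.1.2 states that the design "yields a type I error rate of 0.05 and statistical power of 0.80 for each of the three main cohorts".
- **Interim definition.** SAP 5.4.3.1 takes a minimum of 6 and a maximum of 13 "patients having completed from 9 up to 27 weeks of treatment (3 to 9 cycles) in the colorectal cancer cohort". Sections 5.4.3.2 and 5.4.3.3 repeat this with maxima of 16 and 15, and SAP 3.3.1.2 and Protocol 12.2 carry the same ranges. The continuation thresholds stay at 1, 2 and 2 responses whatever the number of patients in the set.

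One extra patient is enrolled per cohort. Protocol 12.2 says of this patient: "This patient will only be included in the interim analysis in case a patient drops out in that cohort". The same note appears in Protocol 12.7 and SAP 3.3.1.2.

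None of the interim sections names an analysis population or says how to count a patient who progresses, dies or stops before completing 9 weeks. The cervical section gives a maximum of 15 and then a range ending at 16.

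**The concern.** A threshold of r1 responses has the Simon properties only for the n1 it was derived with. If the interim set is restricted to nine-week completers, topped up with a spare, or allowed to be as small as 6, the probability of passing the look changes for ineffective and active drugs alike. SAP 5.4.3 presents this interim as the first stage of the Simon design, and Protocol 3.2.2 gives its purpose as limiting exposure to an ineffective drug. With the denominator undefined, someone must choose it during the trial, in an open-label study where responses are already visible. An ineffective combination could be carried forward somewhat more often than planned, or an active one dropped much more often.

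**Working it through.** **Inputs.** Null rates p0: "5%, 7% and 10% for colorectal cancer, ovarian cancer and cervical cancer, respectively" (Protocol Synopsis, Statistical Considerations). Target rates p1: "true response rate is 20% for colorectal cancer, 25% for ovarian cancer and 30% for cervical cancer" (SAP 3.3.1.2). Design constants from SAP Table 4. The documents give no share d of patients stopping before week 9, so d is an assumption wherever it appears, with no early stopper being a responder. All triplets are colorectal/ovarian/cervical.

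**Step 1. Reproduce the design.** P(reject) = Σ over x > r1 of P(X1 = x | n1, p) · P(X2 ≥ r2 + 1 − x | n − n1, p).
- At p0: 0.042/0.031/0.033. At p1: 0.801/0.803/0.802. The stated 0.05 (an upper limit) and 0.80 are confirmed.
- Probability of continuing, P(X1 > r1 | n1, p). At p0: 48.7/31.0/45.1%. At p1: 94.5/93.7/96.5%. Colorectal at p0, for example: 1 − 0.95^13 = 0.487.

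**Step 2. Early stoppers left out, not replaced.** The rule counts responses, and a removed non-responder contributes none. Continuation at p0 stays at 48.7/31.0/45.1% for every d.

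**Step 3. One early stopper replaced by the documented spare.** At most n1 + 1 patients are then treated before the decision, so the ceiling is P(X > r1 | n1 + 1, p0) = 51.2/33.6/48.5% (colorectal: 1 − 0.95^14 = 0.512). The rise is about 2.6/2.6/3.4 points. With n + 1 patients at the end and r2 unchanged, overall type I error is 0.047/0.036/0.039, still under 0.05.

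**Step 4. Accrual continued until n1 completers exist.** The response rate among completers becomes p0/(1 − d), and continuation is P(X > r1 | n1, p0/(1 − d)):

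| d (assumed) | Colorectal | Ovarian | Cervical |
|---|---|---|---|
| 10% | 52.4% | 35.7% | 50.9% |
| 20% | 56.8% | 41.4% | 57.6% |
| 30% | 61.8% | 48.5% | 65.3% |

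The mean number treated before the look is n1/(1 − d). At d = 20% this is 13/0.8 = 16.3, 16/0.8 = 20.0 and 15/0.8 = 18.8. With total n held at 27/26/25, simulation moves the type I error by 0.002 or less.

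**Step 5. Look at 6 patients, thresholds unchanged.** P(X > r1 | 6, p):
- At p0: 26.5/6.1/11.4%.
- At p1: 73.8/46.6/58.0% (colorectal: 1 − 0.8^6 = 0.738).
- Overall power with 6 patients in stage 1, total n and r2 as planned: 65/44/53%.

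These take p1 as the response rate among the 6. If they are completers and d = 20%, the rate is p1/0.8 = 25/31.25/37.5%, and continuation is 82.2/60.6/72.6%, still well below the design (colorectal: 1 − 0.75^6 = 0.822).

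**Step 6. Timing.** The first scan is at week 9, and SAP 4.2.3.1 requires confirmation at least 4 weeks later. A patient with only 9 weeks of treatment cannot yet be a confirmed responder, which adds to the risk of a false stop at an early look.

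**The case against.** Three points can be made for the plan.

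- **Data maturity.** The 9-to-27-week phrase may describe follow-up under staggered accrual rather than a condition for entering the set. That is a fair reading, and it agrees with the accrual-based rule in SAP 5.6.1. The text does not say so, however, and does not say what happens to those without 9 weeks.
- **Evaluable population.** SAP 5.2.2 keeps patients who die or stop for an adverse event before assessment and treats them as progressed, and SAP 5.6.1 uses that population for the primary endpoint. If it also governs the interim, such patients do count. This stands in part: no population is named for the interim, and a patient who leaves for clinical deterioration or withdrawal without a scan falls outside the rule anyway.
- **Safeguards.** The DMC may delay the look by up to 4 months (Protocol 3.1.4), which softens the early-look problem but does not require all n1. The adjustment in SAP 5.6.1 for a different number of evaluable patients modifies stage 2 only; it keeps n1 and r1 as planned.

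A reader might infer that dropping early failures inflates the apparent response rate and so carries an ineffective drug forward much more often. The documents do not support that. No rate is tested at the interim, and step 2 shows no change from exclusion alone. The large figures in step 4 need replacement without limit. The text provides one spare per cohort and permits fewer than n1 patients; it neither states nor excludes accrual until n1 completers exist.

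**Conclusion.** The contradiction is real and should be resolved before the interim. Its effect depends on the reading adopted.

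- With the one documented spare, continuation at p0 rises by at most about 2.6/2.6/3.4 points and type I error stays below 0.05. This is minor.
- Step 4 is a conditional case, resting on an assumed d and on a replacement practice that is not written down.
- The larger documented exposure is the permitted 6-patient minimum: false futility stops at p1 rise from 5.5/6.3/3.5% to 26.2/53.4/42.0%, and power falls to about 65/44/53%. This assumes the look is actually taken at 6 with r2 and total n unchanged. Intermediate numbers give intermediate losses.

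It would also be wrong to infer that the 5% type I error claim fails. In the documented cases above it holds; what is not secured is the 80% power and the planned futility stopping probability.

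**What to change.** In SAP 5.4.3.1 to 5.4.3.3, SAP 3.3.1.2 and Protocol 12.2:

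- Define the interim set as the first 13/16/15 treated patients in the cohort.
- Count every one of them who progresses, dies or stops without a confirmed response as a non-responder, whatever the number of weeks completed.
- State that the spare does not replace an early stopper at the interim, and amend the matching note in Protocol 12.7.
- Delete the 6-to-n1 range and take the look once all n1 patients can be classified, allowing for the confirmatory scan.
- Correct the upper limit in the cervical section so that 15 and 16 no longer conflict.

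This restores the step 1 values: continuation of 48.7/31.0/45.1% at p0 and 94.5/93.7/96.5% at p1, with power of 0.80. The cost is wording only, with no extra patients or scans. The interim may come somewhat later, and active cohorts keep the design's roughly 4 to 6% chance of a false futility stop.
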